Appendix D.

Patient Questionnaire

**Xarelto Risk Minimization Study
Survey Instructions**

Thank you for agreeing to participate in this study!

Taking part in this study will take approximately 20 to 25 minutes of your time. Your responses will be kept completely confidential and will not be shared with your health care professionals (e.g., surgery or hospital based doctor or nurse).

This survey consists of two questionnaires. Please follow the instructions below to complete the survey. If you have any questions, please ask the study coordinator for help.

Step 1 - Open envelope #1 and complete the first questionnaire. Please do not refer to the Xarelto patient alert card or other Xarelto educational materials while answering the questionnaire.

Step 2 – When you have completed the first questionnaire, place it back into the envelope and seal the envelope.

Step 3 – Open envelope #2. Inside the envelope you will find a Xarelto patient alert card. Please read the Xarelto patient alert card. After you have read it, complete the second questionnaire.

Step 4 - When you have completed the second questionnaire, place it back into the envelope and seal the envelope.

Step 5 – Return both envelopes to the study coordinator.

**Xarelto Risk Minimization Study
Patient Questionnaire #1**

This is the first of two questionnaires. Please complete this questionnaire before moving on to the second questionnaire (found in a separate envelope).

Please answer the following questions first to confirm that you are eligible for this study.

S1. Are you 18 years of age or older?

- Yes
- No (If no, please speak with the study coordinator to confirm your eligibility.)

S2. Have you taken Xarelto (also known as rivaroxaban) in the past 3 months?

- Yes, I have taken Xarelto in the past 3 months
- No, I have not taken Xarelto in the past 3 months
- I don't know

The purpose of this study is to learn more about your knowledge and understanding of the safety information related to Xarelto (rivaroxaban).

Please do not look at the Xarelto patient alert card while answering the following questions.

Q1. Are you currently taking Xarelto?

- Yes
- No
- I don't know

Q2. Approximately how long have you been taking Xarelto?

Select the one answer that best applies to you.

- Less than 1 month
- Between 1 and 6 months
- More than 6 months but less than 1 year
- More than 1 year
- I don't know

Q3. How many prescription medications, including Xarelto, are you currently taking on a regular basis?

Select the one answer that best applies to you.

- I am taking only 1 prescription medication (Xarelto)
- 2 prescription medications
- 3 to 4 prescription medications
- 5 to 6 prescription medications
- More than 6 prescription medications
- I don't know

Q4. Xarelto is a prescription medicine used to thin the blood to prevent blood clots?

- Yes, this is true
- No, this is not true
- I don't know

Q5. Before starting Xarelto, had you ever taken any prescription blood thinners (medications that thin the blood to prevent blood clots)?

- Yes

- No
- I don't know

Q6. Where did you get most of your information about Xarelto?

Select the one answer that best applies to you.

- From my doctor
- From a specialist at the hospital
- From my pharmacist
- From a friend or family member
- From my carer
- From articles in newspapers or magazines
- From the Internet
- From the Xarelto Patient Alert Card and/or patient information leaflet

Other, please specify _____

Like all medicines, Xarelto can cause side effects, although not everybody gets them.

The following questions are to learn more about your knowledge of side effect(s) that people who take Xarelto could potentially experience.

Please note that these questions are not asking about your own experiences while taking Xarelto.

If you have any questions or concerns about the information in the questionnaire, please talk with your health care professional.

Q7. Has your health care professional ever talked to you about the possible side effects of Xarelto?

- Yes
- No
- I don't know

Q8. Blood thinning medications, such as Xarelto, may cause bleeding. Please remember that this question is asking about your knowledge in general and not about your own experience.

- Yes, this is true
- No, this is not true
- I don't know

Q9. Which of the following are possible signs or symptoms of bleeding while taking Xarelto? Please remember that this question is asking about your knowledge in general and not about your own experience.

Check the box Yes, No, or I don't know for each of the following items.

| | Yes, this may be a sign or symptom of bleeding when taking Xarelto | No, this is not a sign or symptom of bleeding when taking Xarelto | I don't know if this is a sign or symptom of bleeding when taking Xarelto |
|-------------------------------------|---|--|--|
| Pain |  |  |  |
| Swelling or discomfort |  |  |  |
| Headache, dizziness, or weakness |  |  |  |
| Unusual bruising |  |  |  |

Q10. I must not stop taking Xarelto at any time without consulting with my doctor.

- Yes, this is true
- No, this is not true
- I don't know

Q11. I need to speak to my doctor prior to any intake of other medication(s).

- Yes, this is true
- No, this is not true
- I don't know

Q12. I need to inform my doctor or dentist about Xarelto intake prior to any kind of surgery or invasive procedure.

- Yes, this is true
- No, this is not true
- I don't know

Q13. I need to tell my doctor right away if I have any signs or symptoms of bleeding while taking Xarelto.

- Yes, this is true
- No, this is not true
- I don't know

Q14. Should Xarelto (15 mg and 20 mg tablets) be taken with food?

- Yes
- No
- I don't know

Q15. What should you do to ensure Xarelto is effective in preventing blood clots?

Select all that apply.

- Take Xarelto exactly as prescribed by your Health Care Professional
- Take Xarelto only when you do not feel well
- Do not miss a dose of Xarelto
- I don't know

In this last section, please tell us a little information about yourself to help us describe the participants completing this questionnaire.

Q16. I was prescribed Xarelto for the following reason(s)...

Select all that apply

- Prevention of stroke
- A blood clot in a vein
- I don't know
- Other _____

Q17. How old are you?

- 18-25 years
- 26-35 years
- 36-45 years
- 46-55 years
- 56-65 years
- 66-75 years
- 76-85 years
- 86 years or older

Q18. Are you ...?

- Male
- Female

Q19. What is the highest level of education you have completed?

Select the one answer that best applies to you.

- Primary school education or less
- Secondary school education (e.g. GCSE/A level, Scottish Standard Grades/Highers)
- Professional or work-related college qualifications (e.g. Certificate of Higher Education, Diploma of Higher Education, foundation degree)
- Undergraduate university degree (e.g. BSc/BA)
- Postgraduate university degree (e.g. MSc/MA, MPhil, PhD)

You have now reached the end of the first questionnaire. Please place your completed questionnaire back into the envelope and seal the envelope. Then, follow the instructions for completion of the second part of the survey.

**Xarelto Risk Minimization Study
Patient Questionnaire #2**

This is the second of two questionnaires. Before you proceed, please make sure you have completed the first questionnaire (found in a separate envelope).

[Patient alert card is included in envelope 2]

The purpose of the second questionnaire is to learn more about your understanding of important safety information related to Xarelto after reviewing the Xarelto Patient Alert Card.

Before you complete this questionnaire, please read through the attached Xarelto Patient Alert Card as if you just had received it for the first time from your doctor.

After you have read the Xarelto Patient Alert Card, please answer the following questions related to the safety information provided in the card.

Q1. Xarelto is a prescription medicine used to thin the blood to prevent blood clots?

- Yes, this is true
- No, this is not true
- I don't know

Q2. Blood thinning medications, such as Xarelto, may cause bleeding. Please remember that this question is asking about your knowledge in general and not about your own experience.

- Yes, this is true
- No, this is not true
- I don't know

Q3. Which of the following are possible signs or symptoms of bleeding while taking Xarelto? Please remember that this question is asking about your knowledge in general and not about your own experience.

Check the box Yes, No, or I don't know for each of the following items.

| | Yes, this may be a sign or symptom of bleeding when taking Xarelto | No, this is not a sign or symptom of bleeding when taking Xarelto | I don't know if this is a sign or symptom of bleeding when taking Xarelto |
|-------------------------------------|---|--|--|
| Pain |  |  |  |
| Swelling or discomfort |  |  |  |
| Headache, dizziness, or weakness |  |  |  |
| Unusual bruising |  |  |  |

Q4. I must not stop taking Xarelto at any time without consulting with my doctor.

- Yes, this is true
- No, this is not true
- I don't know

Q5. I need to speak to my doctor prior to any intake of other medication(s).

- Yes, this is true
- No, this is not true
- I don't know

Q6. I need to inform my doctor or dentist about Xarelto intake prior to any kind of surgery or invasive procedure.

- Yes, this is true
- No, this is not true
- I don't know

Q7. I need to tell my doctor right away if I have any signs or symptoms of bleeding while taking Xarelto.

- Yes, this is true
- No, this is not true
- I don't know

Q8. Should Xarelto (15 mg and 20 mg tablets) be taken with food?

- Yes
- No
- I don't know

Q9. What should you do to ensure Xarelto is effective in preventing blood clots?

Select all that apply.

- Take Xarelto exactly as prescribed by your Health Care Professional
- Take Xarelto only when you do not feel well
- Do not miss a dose of Xarelto
- I don't know

The next section is about the Xarelto Patient Alert Card that you reviewed before completing the second questionnaire. The Xarelto Patient Alert Card contains important safety information about Xarelto.

Q10. Prior to today, had you received or been given the Patient Alert Card for Xarelto?

- Yes → **Go to Q11**
- No → **Go to Q15**
- I don't remember → **Go to Q15**

Answer questions Q11 – Q14 only if you received a Patient Alert Card for Xarelto.

Q11. Prior to today, had you ever read the Patient Alert Card for Xarelto?

- Yes → **Go to Q13**
- No → **Go to Q12**
- I don't remember → **Go to Q13**

Q12. Is there a reason why you have not read the Patient Alert Card for Xarelto, prior to today?

Select all that apply.

- I haven't taken the medication yet
- Someone else explained it to me
- I lost the patient alert card
- I already knew the information
- I have not had the time yet
- I am not interested in reading it
- Other

Q13. How much of the time do you keep the Xarelto Patient Alert Card with you?

Select the one answer that best applies to you

- All the time
- Some of the time
- None of the time
- I don't know

Q14. Who do you show the Patient Alert Card to?

Select the one answer that best applies to you

- Every doctor or dentist that I visit
- No one, it is just for my information
- Only to healthcare professionals who ask for it
- I don't know

Q15. Prior to today, had someone explained the information in the Patient Alert Card for Xarelto to you?

Select all that apply.

- Yes, a doctor
- Yes, a nurse
- Yes, a pharmacist or someone at the chemists
- Yes, a friend, family member, or carer
- No

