3.2.6 Patient Data Collection

The patient questionnaire will be self-administered (closed-ended questions with predefined answers) on hard copy forms at the site. While there are a number of advantages to using an electronic format for questionnaire administration, we anticipate a paper format will be

preferred in this case based on the study population (e.g., older patients). Written informed consent will be obtained from each patient prior to completion of this questionnaire.

Patients will be asked to complete the questionnaire in the physician's office in a private setting. Sites will provide patients with appropriate privacy so there is no influence by the physician (or patient perception thereof) in this process. Patients will be asked to complete the questionnaire without referring to the patient alert card. Once they have completed the questionnaire, the patient will be asked to review the patient alert card and then re-answer selected questions related to key safety information to gather data on patient knowledge immediately after exposure to the card. Patients will then place their completed forms in an envelope and give the sealed envelope to a study coordinator or designee. While participating physicians will be informed of the purpose of the study, they will be counselled not to alter routine practice and patient education so as not to influence the study results. Physicians will be advised that the ultimate goal of the study is to evaluate the educational materials.

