stratify knowledge results based on duration of use, patient use and receipt of the patient alert card, and provider knowledge.

The study will target a total of 1,500 physicians¹ (approximately 300 per country) and 500 patients² (approximately 100 patients per country) to complete the assessment. The majority of the analysis will focus on aggregated data. Although the report may display country-specific findings, there may be limitations with drawing country-specific conclusions, particularly for the patient assessment given the relatively small samples sizes within each country.

As with all voluntary studies, some limitations are inherent. Although the study is designed to ensure the selection of a diverse and generally representative sample of prescribers and patients to participate in this study, there exists no exhaustive list of all rivaroxaban prescribers and patients from which to draw a sample; hence, it is impossible to select a random sample of all prescribers/patients. Therefore, the study participants may not necessarily represent all users of rivaroxaban. In addition, as is true with most surveys, it is possible that respondents who complete the questionnaire will differ from non-respondents in characteristics measured in the questionnaire (e.g., knowledge, reading the educational materials). The direction and magnitude of such potential respondent bias is not known. In addition, the sample does not account for individuals who could not participate because of the mode of data collection (i.e., Internet access). However, it is anticipated that the majority of physicians will be Internet enabled.

Another potential limitation of the patient assessment is that the study could influence sites to provide more education to patients than they normally would provide. To minimize this risk, sites will be trained to provide only limited information about the study prior to the patients' participation in the study, and patients will be asked to complete the questionnaire at the site prior to receiving any additional counseling about treatment. In addition, it is not possible to restrict patients from changing their responses on the paper questionnaire based on information learned as they complete the questionnaire. However, the questionnaire will emphasize that the patients should respond based on what they know and explain that the ultimate goal of the study is to make sure that patients are well informed about their medications.

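### Patient Questionnaire #1 invites patients to take questions about its content to their health care professional without asking them to wait until it is sealed, which leaves an avoidable route for coaching

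*Protocol*

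**What the plan says.** **Intended safeguards.** Section 3.2.6 sets the place: "Patients will be asked to complete the questionnaire in the physician's office in a private setting". It also gives the purpose of the privacy: "Sites will provide patients with appropriate privacy so there is no influence by the physician (or patient perception thereof) in this process". Section 5 recognises that the study could lead sites to educate patients more than usual. Among its countermeasures, "patients will be asked to complete the questionnaire at the site prior to receiving any additional counseling about treatment". It adds that "the questionnaire will emphasize that the patients should respond based on what they know".

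**The form the patient reads (Appendix D).** The cover sheet restricts materials only: "Please do not refer to the Xarelto patient alert card or other Xarelto educational materials while answering the questionnaire". Before listing the envelope steps it offers help: "If you have any questions, please ask the study coordinator for help". In Questionnaire #1, after Q6, the next block is announced: "The following questions are to learn more about your knowledge of side effect(s) that people who take Xarelto could potentially experience". Two sentences later comes: "If you have any questions or concerns about the information in the questionnaire, please talk with your health care professional". Q7 then asks whether a professional has ever discussed side effects. The scored items follow as Q8–Q15: bleeding risk and signs, stopping, other medicines, surgery, reporting bleeding, food, and taking the drug as prescribed. After sealing this form the patient reads the card, and Questionnaire #2 repeats those eight items as Q2–Q9.

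**The concern.** Questionnaire #1 is the only record of what patients know before the study itself shows them the card. A sentence that points them to their clinician, printed mid-form, with no time attached and in that clinician's practice, leaves room to ask before answering. Patients who did so and were told the answer would be counted as already informed. That would raise the pre-card percentage correct and leave less for the card to improve. The effect could also differ between practices, depending on how readily staff respond. A confidence interval does not cover a bias of this kind, and recruiting more patients does not reduce it.

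**Working it through.** **1. The passages side by side**

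| Question | Protocol body | Appendix D |
|---|---|---|
| May the clinician be consulted before the form is finished? | Aim of no physician influence (3.2.6); questionnaire before further counselling (5) | Referral to the professional, no timing; the order rule does not appear |
| What is off limits while answering? | The card (3.2.6) | The card and other educational materials; asking a person is not mentioned |
| Is the patient told to answer from own knowledge? | Promised (5) | A statement that the study is about the patient's knowledge, and reminders at Q8 and Q9 that general knowledge rather than personal experience is meant; no direct instruction |

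The physician form in Appendix C is ordered differently: its offer of further information and the Prescriber Guide link come after the closing thank-you. The patient form places its comparable offer in the middle.

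The sentence precedes Q8–Q15 only. Knowledge item Q4 comes before it, and Q7 is not a knowledge item.

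**2. The plan's precision, reproduced**

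Inputs from Section 3.2.4 and Table 2: n = 500; p = 50% or 80%; design effect DE = 1 (intraclass correlation 0) or 4 (0.33).

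Half-width = 1.96 × √(p(1 − p) × DE / n)

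- p = 0.5, DE 1: 1.96 × √(0.25/500) = 4.4 points, so 45.6–54.4%, as printed.
- p = 0.5, DE 4: 8.8 points, so 41.2–58.8%, as printed.
- p = 0.8, DE 1: 1.96 × √(0.16/500) = 3.5 points, so 76.5–83.5%, as printed.
- p = 0.8, DE 4: 7.0 points, so 73.0–87.0%, as printed.

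**3. Size of the possible bias**

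The documents give no coaching rate. Let c be the share of patients *who do not know an item* and are given the answer before responding. The definition matters: patients who already know cannot be moved.

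Rise in pre-card percentage correct = c × (1 − p)

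| Assumed c | p = 50% | p = 80% |
|---|---|---|
| 2% | 0.02 × 0.5 = 1.0 point | 0.02 × 0.2 = 0.4 point |
| 5% | 2.5 points | 1.0 point |
| 10% | 5.0 points | 2.0 points |
| Half-width, n = 500, DE 1 to 4 | 4.4 to 8.8 points | 3.5 to 7.0 points |

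**4. Coaching rate at which the bias equals the half-width**

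c = half-width / (1 − p)

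- At 50% correct: 4.4/0.5 = 8.8% with no clustering; 8.8/0.5 = 17.6% at DE 4.
- At 80% correct: 3.5/0.2 = 17.5%; 7.0/0.2 = 35%.

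**5. Before/after-card difference**

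Coaching removes an apparent gain only for patients who would have been wrong before the card and right after it. The difference therefore shrinks by at most c × (1 − p), the figures in step 3.

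**The case against.** The strongest reply is that the sentence is a safety referral. It closes a notice about side effects and is addressed to patients whom that content may worry. It does not tell anyone to consult before answering, and a referral with no time attached can be reconciled with counselling after the form. Several features also work against coaching:

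- completion is private;
- physicians are counselled not to change their routine practice or patient education;
- sites are trained to say little about the study beforehand and to have the form completed before further counselling;
- every item from Q8 to Q15 has a don't-know option, so an unsure patient can answer without help.

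The coordinator line follows the request to work through the listed steps and reads most naturally as help with procedure. Section 5 already names extra education by sites as a limitation. The knowledge items are also only part of the patient objective: receipt, reading and carrying of the card are asked in Questionnaire #2.

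Most of this stands, and it limits how far the point goes. A reader might infer that the form flatly contradicts the protocol, or that unsure patients will ask and be told the answer. The documents support neither: the form permits consultation, and whether it happens is unknown.

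What the reply does not remove is the mismatch. The order rule is addressed to sites, while the patient sees only Appendix D, where the rule is absent and the one sentence about talking to the professional is open in time. The training described concerns what sites say before participation, not how to respond to a patient who, following the printed text, asks partway through.

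**Conclusion.** The point holds as a wording weakness that leaves an avoidable route for bias. The mid-form referral fits badly with the aims in Sections 3.2.6 and 5, and Appendix D does not clearly carry the answer-from-own-knowledge instruction that Section 5 promises. Coaching would raise pre-card knowledge and could shrink the before/after-card difference.

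The size cannot be derived from the documents. The range of 1–5 points at 50% correct and 0.4–2 points at 80% rests wholly on the assumption that 2–10% of not-knowing patients are coached. Within that range the bias exceeds a planned half-width only at 50% correct, near the top of the range and with no clustering. With the clustering the plan allows for, or at 80% correct, it stays below. Given the private setting, the training and the don't-know options, the real effect may be small. A reader might infer that the pre-card results would be invalid; nothing here supports that. The case for acting is that the remedy is cheap and the bias, if present, could not be separated from true knowledge afterwards.

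**What to change.** - Keep the referral, but move it from before Q7 in Questionnaire #1 to the end of Questionnaire #2, worded on these lines: *Once you have sealed both envelopes, please raise any questions about what you have read with your health care professional.*
- On the cover sheet and in site training, state that until both envelopes are sealed the coordinator can explain how to fill in the forms but cannot help with answers. This should cover questions about the content of the forms only; the handling of reported adverse reactions in Section 3.4 stays as it is.
- Add to the start of Questionnaire #1 the line that Section 5 promises, for example: *Please answer from your own knowledge; if you are unsure, tick the don't-know box.*

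The cost is a wording change in Appendix D and its translations, any ethics notification or review required in each country, and a line in site training. A patient with a question about the content waits at most the 20 to 25 minutes that the cover sheet gives for the survey.

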3.2.5 Patient Questionnaire Development

The patient questionnaire has also been developed following standard survey methodologic principles and has been cognitively tested with patients in each of the target countries. Modifications have been made to the questionnaire based on the results of testing and additional feedback from the sponsor. The final version of the questionnaire can be found in Appendix D. Some modifications to the questionnaire are anticipated based on country-specific requirements. The questionnaire will assess patient knowledge of the following concepts:

- Receipt and use of the patient alert card
- Knowledge of the key safety messages outlined in the patient alert card:
 - Signs or symptoms of bleeding and when to seek attention from a health care provider
 - Importance of treatment compliance
 - Necessity of taking the 15-mg and 20-mg tablets with food
 - Necessity of carrying the patient alert card at all times
 - Necessity of informing HCPs that they are taking rivaroxaban if they need to have surgery or invasive procedures

The questionnaire includes demographics and other patient information to help characterise patterns of knowledge and behaviour through stratification of results. The questionnaire has been designed to take approximately 20 minutes to complete.

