Appendix B.
Xarelto Patient Alert Card

What should I know about Xarelto®?

- Xarelto® thins the blood, which prevents you from dangerous blood clots.
- Xarelto® must be taken exactly as prescribed by your doctor. To ensure optimal protection from blood clots, **never skip a dose.**
- You must not stop taking Xarelto® without first talking to your doctor as your risk of blood clots may increase.
- Speak to your health care provider prior to any intake of other medication.
- Inform your health care providers about Xarelto® intake prior to any surgery or invasive procedure.

When should I seek advice from my health care provider?

When taking a blood thinner such as Xarelto® it is important to be aware of its possible side effects. Bleeding is the most common side effect. Do not start taking Xarelto® if you are at risk of abnormal bleeding, without first discussing this with your doctor.

Tell your health care provider right away if you have any signs or symptoms of bleeding such as the following:

- pain
- swelling or discomfort
- headache, dizziness or weakness
- unusual bruising, nosebleeds, bleeding of gums, bleeding from cuts that take a long time to stop

- menstrual flow or vaginal bleeding that is heavier than normal
- pink or brown urine, red or black stools
- coughing up blood, or vomiting blood or material that looks like coffee grounds.

How do I take Xarelto®?

- To ensure optimal protection, Xarelto® 15mg and 20mg must be taken with food.

Date of preparation: November 2012
L.GB.10.2012.0954

PATIENT ALERT CARD

Xarelto® 15mg
Xarelto® 20mg

- **Keep this card with you at all times**
- **Present this card to every physician or dentist prior to treatment**

I am under anticoagulation treatment with Xarelto® (rivaroxaban)

Name: _____

Address: _____

Birth date: _____

Blood type: _____

Weight: _____

Other medications/conditions: _____

In case of emergency, please notify:

Doctor's name: _____

Doctor's phone: _____

Doctor's stamp: _____

Please also notify:

Name: _____

Phone: _____

Relationship: _____

Information for health care providers:

- INR values should not be used as they are not a dependable measure of the anticoagulant activity of Xarelto®.

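### The patient bleeding-sign grid omits the alert card's visible-blood signs and expects Yes on every row, so a high result cannot be told apart from yes-saying

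*Protocol*

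**What the plan says.** Section 3.2.5 sets out what the patient questionnaire must cover. The first key message from the card is "Signs or symptoms of bleeding and when to seek attention from a health care provider".

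The card (Appendix B) introduces its list with "Tell your health care provider right away if you have any signs or symptoms of bleeding such as the following" and gives seven bullets. The first three are pain, swelling or discomfort, and headache with dizziness or weakness. The fourth groups several signs together: "unusual bruising, nosebleeds, bleeding of gums, bleeding from cuts that take a long time to stop". The fifth concerns unusually heavy periods or other vaginal blood loss. The sixth, on discoloured excretions, reads "pink or brown urine, red or black stools". The seventh and last deals with blood that the patient coughs or vomits up.

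Appendix D, Questionnaire #1 Q9 asks which items are possible signs of bleeding, with Yes, No and I don't know for each. Its four rows are pain, swelling or discomfort, "Headache, dizziness, or weakness" and "Unusual bruising". Questionnaire #2 Q3, answered after the patient reads the card, has the same four rows. It is printed there as one continuous table, so the short list is not an effect of a page break.

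**The concern.** Two features of the grid limit what it can show.

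The first is coverage. The rows stop partway through the card's fourth bullet. Nosebleeds, gum bleeding, slow-stopping cuts, heavier menstrual or vaginal bleeding, discoloured urine or stools, and coughed or vomited blood are never asked about. Bruising is a sign the patient can see, but no row concerns blood that the patient sees being lost.

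The second is direction. All four rows come from the card, so Yes is the right answer every time. The comparable physician item (Appendix C, Q6) includes a row on chronic constipation, which is not among the prescriber guide's higher-risk groups and so acts as a foil. The patient grid has no such row.

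At stake is how a favourable result is read. If most patients tick Yes on all rows, the report cannot say how much of that is knowledge, and it cannot say whether the card conveys the visible-blood signs. No later analysis can recover signs that were not asked about.

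**Working it through.** **Coverage.** Inputs: the card list (Appendix B) and the grid rows (Appendix D).

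| Card bullet | In the grid? |
|---|---|
| 1. Pain | Yes |
| 2. Swelling or discomfort | Yes |
| 3. Headache, dizziness, weakness | Yes |
| 4. Bruising, nosebleeds, gums, cuts | Bruising only |
| 5. Menstrual or vaginal bleeding | No |
| 6. Urine, stools | No |
| 7. Coughed or vomited blood | No |

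Three bullets are covered in full, one in part and three not at all. Counting bullets 6 and 7 as one sign each gives 3 + 4 + 1 + 1 + 1 = 10 signs. Splitting each of them in two gives 12. The grid covers 4/10 = 40% or 4/12 = 33%.

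**Direction.** No answer key is printed, so the key is inferred from the card. All four rows are on it, which leaves no row where No agrees with the card. The other yes/no knowledge items in Questionnaire #1 run the same way: Q4, Q8 and Q10 to Q14 all have Yes as the card-consistent answer. With the four grid rows that is 1 + 1 + 5 + 4 = 11 of 11. The only wrong option on the form is in Q15, a tick-all question on compliance.

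**Planned precision.** Section 3.2.4 gives the precision for one patient item. The formula is p ± 1.96 × √(p(1−p) × DE / n), with the footnote's design effects (DE) of 1 and 4 for intraclass correlations of 0 and 0.33.

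- n = 500, p = 50%, DE = 1: 1.96 × √(0.25/500) = 4.4 points, or 45.6% to 54.4%. This matches the text.
- n = 500, p = 50%, DE = 4: 1.96 × √(1/500) = 8.8 points, or 41.2% to 58.8%. This matches too.
- n = 500, p = 80%: half-widths of 3.5 points (DE = 1) and 7.0 points (DE = 4), as in Table 2.

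These intervals describe sampling error only.

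**Yes-saying (illustration).** Let k be the share who know a sign and a the share of the others who tick Yes. The documents give neither, so both are assumptions. The observed share is k + (1−k)a.

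| Assumed k | a = 0 | 0.25 | 0.5 | 0.75 | 1 |
|---|---|---|---|---|---|
| 20% | 20% | 40% | 60% | 80% | 100% |
| 50% | 50% | 62.5% | 75% | 87.5% | 100% |
| 80% | 80% | 85% | 90% | 95% | 100% |

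At k = 50% and a = 0.5 the shift is 25 points, and a larger sample does not reduce it. An observed 80% fits k = 80% with a = 0 as well as k = 20% with a = 0.75.

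**Before and after the card.** In the same example the first round shows 75%, which leaves at most 25 points of visible gain where the true room is 50. Yes-saying in both rounds hides improvement; it does not create it.

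**What a foil adds.** Suppose knowers reject the foil and non-knowers tick Yes on it at rate a. The foil's Yes rate is then (1−k)a, and row rate minus foil rate is k + (1−k)a − (1−k)a = k. In the example, 75% − 25% = 50%.

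**The case against.** A reader might infer that the grid says nothing about whether patients know the bleeding message. The documents do not support that. Each row offers No and I don't know, and those answers do show lack of knowledge. The message also has parts outside the grid: Q8 asks whether the medicine may cause bleeding, and Q13 asks about telling the doctor right away. Both stay informative, although Yes is again the expected answer and neither asks which signs indicate bleeding.

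A reader might also call the three non-specific rows a fault because a patient who knows only visible signs would do badly on them. That does not follow. The card lists those signs first, so a low result on them is a valid finding. They are also harder to guess, which is a defensible reason for choosing them.

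Nor does the protocol define a four-out-of-four score. Section 4 plans review of individual questions and only a potential summary measure. The limitation therefore applies to each row's percentage and does not depend on a total.

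Two practical objections also stand. Several omitted signs name blood or bleeding in their own wording, so as rows in a question about signs of bleeding they would largely answer themselves and draw more Yes ticks. And the questionnaire is described as final after cognitive testing (section 3.3, 25 patients across five countries), so a new row would be untested.

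The wrong option in Q15 gives some check on indiscriminate ticking. It concerns compliance, however, and sits in a different response format, so it does not measure yes-saying on the bleeding signs.

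**Conclusion.** The point holds in a limited form. The grid tests 4 of 10 to 12 card signs and none of the visible-blood signs, and it has Yes as the card-consistent answer on all four rows. So a high grid result cannot be told apart from yes-saying, and recognition of the omitted signs is not measured in either round. A low result can still be read as lack of knowledge of the signs that were asked.

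The counts come directly from Appendices B and D, and the direction of the key is inferred from the card. The size of any inflation is unknown: the 25-point example rests wholly on assumed values, and at 50% true knowledge the possible shift runs from 0 to 50 points. This is a weakness of item selection on the first-listed safety message. It does not undermine the rest of the patient assessment.

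**What to change.** Keep the four rows unchanged. In Questionnaire #1 Q9 and Questionnaire #2 Q3:

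- Add a row in the card's own wording, "pink or brown urine, red or black stools". It covers a visible-blood sign without containing its own answer.
- Add at least one foil row, as physician Q6 does with chronic constipation. The card's list is introduced as examples, so absence from the card is not enough; the foil must be something that could not reasonably be taken for a sign of bleeding.
- Report the foil's Yes rate beside the row-level results in both rounds. Subtracting it, as in the illustration, assumes equal yes-saying on foil and true rows. One foil gives only a rough gauge, so show the rates side by side first.

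The cost is two extra rows in an existing grid, translation, ethics notification and a brief wording check in each country. Assessments are planned at 18 months, 3 years and 7 years. The existing rows stay comparable across waves, while the new rows have results only from the wave in which they are introduced.
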